## Primary PK

- o area under the plasma concentration-time curve (AUC) from time 0 to infinity  $(AUC_{0-\infty})$  (actual and dose normalized [DN])
- AUC from time 0 to the time of the last quantifiable concentration (AUC0-tlast) (actual and DN)
- o maximum observed plasma concentration (Cmax) (actual and DN)

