#### 4.1. Part A

Part A will comprise a single-dose, sequential-group design. Overall, 68 healthy subjects will be studied in 11 groups.

Potential subjects will be screened to assess their eligibility to enter the study within 28 days prior to the first dose administration. Potential subjects for Groups A2, A4, A6, A9, A10, and All will attend a pre-screening visit for an intradermal capsaicin test.

Each subject will participate in 1 treatment period only, and will reside at the Clinical Research Unit (CRU) from Day -2 (2 days before dosing) to Day 3. All subjects will return for non-residential visits on Days 4, 7 (±2 days), 10 (±2 days), and 14 (±2 days), and for a poststudy visit on Day 28 (±2 days).

Based on the ongoing review of the safety and tolerability, additional non-residential visits may be required. The number of additional visits per subject will not exceed 3 and will not extend beyond Day 28 (±2 days).

Doses will be administered in an escalating manner following satisfactory review of safety and tolerability data up to Day 10 (216 hours postdose) from the lower dose levels. For doses ≥12 µg, PK data will also be reviewed up to Day 7 prior to dose escalation.

In Part A, Groups A1, A3, A5, A7, and A8 will consist of 4 subjects; 3 subjects will receive OLP-1002 and 1 subject will receive placebo. To assess PD parameters, Groups A2, A4, A6, A9, A10, and A11 will consist of 8 subjects; 6 subjects will receive OLP-1002 and 2 subjects will receive placebo.

Sentinel dosing will be employed for all groups in Part A. To maintain the blind in a 4-subject group, the first subject will be dosed 48 hours before the second subject, and the second subject will be dosed 48 hours prior to the third and fourth subjects. In PD assessment groups, 2 subjects (1 active: 1 placebo) will be dosed 48 hours before the remaining 6 subjects (5 active: 1 placebo).

The total duration of study participation for each subject (from Screening through Follow-up visit) is anticipated to be approximately 8 weeks.

A schematic of the study design is presented in Figure 1.

Figure 1: Study Design (Part A)

Active = OLP-1002; SC = subcutaneous 6 groups consist of 8 subjects (6 active: 2 placebo); all other groups will consist of 4 subjects (3 active: 1 placebo).

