## Part B

Parameter	Definition		
AUC 0-τ	area under the plasma concentration-time curve calculated over the dosing interval		
	$(\tau)$		
$\mathrm{AUC}_{0\text{-}\infty}$	area under the plasma concentration-time curve from time 0 extrapolated to infinity		
$%AUC_{extrap}$	percentage of AUC that is due to extrapolation from the last measurable plasma		
	concentration to infinity		
$C_{max}$	maximum observed plasma concentration		
$C_{trough}$	concentration observed at the end of the dosing interval		
$t_{max}$	time of maximum observed plasma concentration		
$t_{1/2}$	apparent plasma terminal elimination half-life		
$RAAUC_{0-\tau}$	observed accumulation ratio based on AUC 0-τ , calculated as AUC 0-τ on profile day		
	15 / AUC 0-τ on profile day 1		
$RAC_{max}$	observed accumulation ratio based on C max , calculated as C max on profile day 15 /		
	C max on profile day 1		
TCP	temporal change parameter, calculated as $AUC_{0-\tau}$ on profile day 15 / $AUC_{0-\infty}$ on		
	profile day 1		

The DN AUC0-∞, DN AUC0-tlast and DN Cmax will be calculated by dividing the original PK parameter by dose.

Additional PK parameters may be determined where appropriate.

The PK analysis will, where possible, be carried out using actual postdose times recorded in the raw data. If actual times are missing, nominal times may be used.

Concentrations are used as supplied by the analytical laboratory for PK analysis. The units of concentration and resulting PK parameters, with amount or concentration in the unit, will be presented as they are received from the analytical laboratory.

Cmax and tmax will be obtained directly from the plasma concentration-time profiles.

For multiple peaks, the highest postdose concentration will be reported as  $C_{max}$ . In the case that multiple peaks are of equal magnitude, the earliest  $t_{max}$  will be reported.

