#### 8.5.1.3. Calculation of AUC

- The minimum requirement for the calculation of AUC will be the inclusion of at least 3 consecutive plasma concentrations above the lower limit of quantification (LLOQ), with at least 1 of these concentrations following Cmax.
- For any partial AUC determination (i.e. AUC over a dosing interval), nominal time will generally be used for the end of the interval. Actual times for partial AUC intervals may be used at the discretion of the Pharmacokineticist.

• AUC0-∞ values where the percentage extrapolation <20% will be reported. AUC0-∞ values where the percentage extrapolation is between 20 to 30% will be flagged and included in the summary statistics, whilst AUC0-∞ values where the percentage extrapolation is >30% will be reported and flagged but excluded from summary statistics.

• If AUC0-∞ cannot be determined for all subjects or all dose levels, an alternative AUC measure, such as AUC to a fixed time point, may be used in the assessment of dose proportionality.

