## 8.5.1.4. Anomalous Values

- If a value is considered to be anomalous due to being inconsistent with the expected PK profile, it may be appropriate to exclude this point from the PK analysis. However, the exclusion of data must have strong justification and will be documented in the raw data and CSR.
- Embedded BLQ values may be considered anomalous depending on the route of administration and the characteristics of the drug.
- Positive predose value(s) >5% of Cmax may be excluded from the summary statistics of PK tables and statistical analysis at the discretion of the pharmacokineticist.

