## 8.5.3. Pharmacokinetic Statistical Methodology

All PK concentrations and parameters will be listed.

Summary tables, mean (+ standard deviation [SD]) figures, overlaying individual figures, and individual figures by treatment and time postdose will be provided for plasma PK concentrations. All figures will be produced on both linear and semi-logarithmic scales, with the exception of figures across all days (for Part B only), which will be produced on the linear scale only. The +SD bars will be only displayed on the linear scale.

SAP CONFIDENTIAL

Covance Study: 8379789 Protocol Reference: OLP-1002-001

Summary tables by treatment will be provided for all PK parameters, with the exception of regression-related PK parameters.

No inferential statistical analyses are planned.

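### The SAP refers to a dose-proportionality assessment but plans only per-dose summaries, so any departure from proportionality can be judged only by eye, without an estimate or interval

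*SAP*

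**What the plan says.** - **Section 8.5.1.3 (Calculation of AUC)** covers the case where AUC to infinity cannot be determined for all subjects or dose levels: "an alternative AUC measure, such as AUC to a fixed time point, may be used in the assessment of dose proportionality". This is the only mention of dose proportionality in the SAP.
- **Section 8.5.1.4 (Anomalous Values)** says that positive predose values above 5% of Cmax "may be excluded from the summary statistics of PK tables and statistical analysis at the discretion of the pharmacokineticist". That wording treats a PK statistical analysis as something separate from the summary tables.
- **Section 3.2 (Exploratory Endpoints)** lists AUC and Cmax, actual and dose-normalised, under Primary PK sub-headings for both parts. Section 8.5.1 says that dose-normalised values "will be calculated by dividing the original PK parameter by dose".
- **Section 8.5.3 (Pharmacokinetic Statistical Methodology)** provides listings, concentration tables and figures, and this for the parameters: "Summary tables by treatment will be provided for all PK parameters, with the exception of regression-related PK parameters". It ends: "No inferential statistical analyses are planned".
- **Section 4.1 (Part A)** sets the group sizes: "Groups A1, A3, A5, A7, and A8 will consist of 4 subjects; 3 subjects will receive OLP-1002 and 1 subject will receive placebo" and "Groups A2, A4, A6, A9, A10, and A11 will consist of 8 subjects; 6 subjects will receive OLP-1002 and 2 subjects will receive placebo".

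**The concern.** The SAP sets rules for the inputs to an assessment (which AUC may be substituted, which values may be left out) and then does not describe the assessment. No model, dose range, summary measure or display is named.

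Dose normalisation exists so that exposure can be compared across doses, yet no cross-dose quantity is planned. The reader of the report would get a row of dose-normalised summaries, each from 3 or 6 people, and would have to decide by eye whether they drift. That also ignores the fact that all active subjects lie on one ordered dose scale.

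At stake is whether the planned report can say how far exposure departs from proportionality, and with what uncertainty. There is a smaller risk too. Because neither the substitute AUC nor its time point is fixed, both can be chosen after the data are seen.

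**Working it through.** **Check on the plan's own figure.** Section 4.1 gives 68 subjects in 11 groups: 5 × 4 + 6 × 8 = 68, which reproduces. Active subjects: 5 × 3 + 6 × 6 = 51. The SAP states no precision for any PK comparison, so there is no further figure to reproduce.

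**Inputs from the SAP.** Planned Part A doses (section 6.1, Table 1), with active n from section 4.1: 30 ng (3), 120 ng (6), 400 ng (3), 1.2 µg (6), 3 µg (3), 6 µg (6), 12 µg (3), 20 µg (3), 40 µg (6), 80 µg (6), 160 µg (6).

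**Assumed inputs.** Between-subject CV is taken as 40%, with 60% as a check. The lowest dose with usable profiles is taken as 3, 12 or 40 µg. Groups A9 to A11 are assumed to be run: section 5 says they will be, while the Table 1 footnote says only if required.

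**Formulas.** σ = √ln(1 + CV²). At CV 40%, σ = √ln 1.16 = 0.385.

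- *Power model*, ln(parameter) = a + b ln(dose): SE(b) = σ/√Sxx, where Sxx is the sum of squares of ln(dose) about its mean over the N active subjects. The 90% CI for b is ± t(0.95, N − 2) × SE(b). The factor over a dose range r is exp(half-width × ln r).
- *End doses only*, ratio of dose-normalised geometric means: SE = σ√(1/n₁ + 1/n₂) and factor = exp(t × SE). The degrees of freedom are n₁ + n₂ − 2 if only those two groups supply the variance, or N minus the number of doses if it is pooled over all included doses.

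**From 3 µg** (N = 33, 7 doses, r = 53.3, ln r = 3.977, Sxx = 57.29):
- Model: SE(b) = 0.385/7.569 = 0.051. With t₃₁ = 1.696 the half-width is 0.086, and exp(0.0863 × 3.977) = 1.41.
- End doses, 6 v 3: SE = 0.385 × √(1/3 + 1/6) = 0.272. With t₇ = 1.895 the factor is exp(0.516) = 1.68. With pooled variance, t₂₆ = 1.706, it is exp(0.465) = 1.59.

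**From 12 µg** (N = 24, 5 doses, r = 13.3, ln r = 2.590, Sxx = 18.29):
- Model: SE(b) = 0.090, t₂₂ = 1.717, half-width 0.155, factor exp(0.401) = 1.49.
- End doses, 6 v 3: 1.68. Pooled, t₁₉ = 1.729: exp(0.471) = 1.60.

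**From 40 µg** (N = 18, 3 doses, r = 4, ln r = 1.386, Sxx = 5.77):
- Model: SE(b) = 0.160, t₁₆ = 1.746, half-width 0.280, factor exp(0.388) = 1.47.
- End doses, 6 v 6: SE = 0.385 × √(1/3) = 0.222. With t₁₀ = 1.812 the factor is exp(0.403) = 1.50. Pooled, t₁₅ = 1.753: exp(0.390) = 1.48.

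| Lowest usable dose | CV | Power model | End doses, pooled to two-group variance |
|---|---|---|---|
| 3 µg | 40% | ×/÷1.41 | ×/÷1.59 to 1.68 |
| 12 µg | 40% | ×/÷1.49 | ×/÷1.60 to 1.68 |
| 40 µg | 40% | ×/÷1.47 | ×/÷1.48 to 1.50 |
| 3 µg | 60% | ×/÷1.64 | ×/÷1.95 to 2.10 |

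The model gains most when many dose levels are usable and the lowest has only three active subjects. With three doses of six subjects each, the middle dose adds almost nothing to the slope, and the two approaches nearly coincide.

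**The case against.** The strongest reply is that a descriptive-only analysis was a deliberate choice. PK, PD and safety all carry the same statement that no inference is planned, and section 5 makes no formal sample-size claim. Section 2 makes PK exploratory and conditional on feasibility. Dose proportionality is not an objective or an endpoint, its one mention is permissive, and the Primary PK label sits inside the exploratory endpoints. An assessment need not be inferential: dose-normalised tables are a descriptive assessment. Individual values will be listed, and section 1 allows additional analyses identified in the report, so a slope could still be fitted later.

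Most of this stands, and it limits the weight of the point. The SAP does not rest any conclusion on proportionality, and sections 8.5.1.3 and 8.5.3 can be read together without outright contradiction. What remains is that the assessment has no stated method, and that the planned outputs contain no cross-dose estimate or interval. A slope added afterwards would carry choices of AUC, interval and dose range made with the data in view.

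The precision argument also has limits. Part of the model's advantage over a two-group comparison disappears once the comparison uses pooled variance, and the rest is bought by assuming one constant slope.

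A reader might infer that the gap weakens the primary exposure-limit endpoint or the dose decisions in Part B. The SAP does not support either inference. The endpoint in section 3.1 sets exposure against pre-defined non-clinical limits, which needs absolute exposure and not a slope. Part B decisions rest on continuing review of available data (sections 4.2 and 9), before any final regression could be run.

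**Conclusion.** The point holds as a gap in an exploratory analysis. Section 8.5.1.3 provides for an assessment that section 8.5.3 does not specify, and the planned per-treatment summaries let proportionality be judged only by eye. A slope with an interval can be estimated from the subjects already planned.

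The size of the benefit is uncertain. At an assumed CV of 40%, the CI factor narrows clearly if profiles are usable from 3 µg (1.41 against 1.59 to 1.68), moderately from 12 µg (1.49 against 1.60 to 1.68), and hardly at all from 40 µg (1.47 against 1.48 to 1.50). These figures assume equal log-scale variance at every dose, log-linearity, all planned groups run and every active subject evaluable. Even where precision barely improves, the prespecified estimate still replaces an undefined judgement with a stated one.

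**What to change.** In section 8.5.3, add for Part A an exploratory, estimation-only power model, ln(parameter) = a + b ln(dose):

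- **Parameters.** Fit Cmax and one AUC taken over the same prespecified interval at every included dose. AUC to the last quantifiable time is unsuitable because its interval can differ between doses.
- **Reporting.** Give b with its 90% CI and the implied departure from proportionality over the fitted dose range, with no hypothesis test.
- **Dose levels.** Use all evaluable active subjects at levels that meet a stated minimum, so that one non-evaluable subject does not automatically remove a level. The SAP's own threshold of three (section 8.1.1) is one option. It protects the six-subject levels, but a level with three active subjects would still drop out if one were lost, so the sponsor should choose the minimum knowingly. Report the number evaluable at each dose.
- **Check.** Plot residuals against dose to examine log-linearity.
- **Wording.** Keep the descriptive tables, and align sections 8.5.1.3, 8.5.1.4 and 8.5.3 so that all refer to the same analysis.

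If the sponsor prefers summaries only, the minimum is one sentence saying that proportionality is judged descriptively from dose-normalised values, with matching edits to 8.5.1.3 and 8.5.1.4.

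The cost is about one paragraph and one regression per parameter, with no added subjects or samples. The downside is the log-linearity assumption.

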## 8.5.1.4. Anomalous Values

- If a value is considered to be anomalous due to being inconsistent with the expected PK profile, it may be appropriate to exclude this point from the PK analysis. However, the exclusion of data must have strong justification and will be documented in the raw data and CSR.
- Embedded BLQ values may be considered anomalous depending on the route of administration and the characteristics of the drug.
- Positive predose value(s) >5% of Cmax may be excluded from the summary statistics of PK tables and statistical analysis at the discretion of the pharmacokineticist.

#### 8.5.2. Presentation Pharmacokinetic Plasma Concentration Data

- The following rules will be applied if there are values that are BLQ or if there are missing values in a plasma concentration data series to be summarized.
  - o For the calculation of summary statistics, BLQ values will be set to 0.
  - o If an embedded BLQ value is considered anomalous within the concentration-time profile, this value will be excluded from the summary statistics.
  - If the value of the arithmetic mean or median is BLQ, these values will be presented as 0 and the geometric mean and geometric coefficient of variation will not be calculated.
  - o Concentrations collected with a time deviation from nominal time >10% will be reported and flagged but excluded from summary statistics.

## 8.5.3. Pharmacokinetic Statistical Methodology

All PK concentrations and parameters will be listed.

Summary tables, mean (+ standard deviation [SD]) figures, overlaying individual figures, and individual figures by treatment and time postdose will be provided for plasma PK concentrations. All figures will be produced on both linear and semi-logarithmic scales, with the exception of figures across all days (for Part B only), which will be produced on the linear scale only. The +SD bars will be only displayed on the linear scale.

SAP CONFIDENTIAL

Covance Study: 8379789 Protocol Reference: OLP-1002-001

Summary tables by treatment will be provided for all PK parameters, with the exception of regression-related PK parameters.

No inferential statistical analyses are planned.

## 8.6. Pharmacodynamic Assessments (Part A Only)

Capsaicin intradermal test will be performed for subjects in Groups A2, A4, A6, A9, A10 and A11. Each subject will be tested at a pre-screening visit before being tested twice during the study (1 predose and 1 postdose).

## 8.6.1. Capsaicin-evoked Pain Model

The capsaicin model will be conducted by intradermal injection of capsaicin (100  $\mu$ g in 100  $\mu$ L of sterile saline containing 8% [w/w] Tween 80) into the skin of the anterior aspect of the forearm, midway between the elbow and the wrist. The bleb area (wheal) will be a sign of local plasma extravasation. An assessment of the pain intensity related to capsaicin injection will be estimated by repeated use of a VAS from injection to 5 minutes post-injection or until the pain intensity returned to 0. The AUC,  $E_{max}$ , and  $tE_{max}$  will be calculated and reported using dedicated software.

## 8.6.2. Secondary Hyperalgesia

The area of secondary hyperalgesia will be quantified with a 60-g weighted von Frey hair, by stimulating along 8 linear paths (4 vectors crossing at the location of the injection site) arranged vertically and horizontally around the stimulation site in 5-mm steps (starting approximately 6 cm away from the injection site). The area of secondary hyperalgesia will be evaluated at 5 and 30 minutes post-capsaicin injection.

## 8.6.3. Pharmacodynamic Statistical Methodology

All PD data and parameters will be listed.

Summary tables and mean figures by treatment and timepoint will be provided for all PD parameters.

Values recorded as  $\langle x, \leq x, \rangle x$ , or  $\geq x$  will be displayed in the listings as recorded. For the derivation of listing flags, calculation of summary statistics, and presentation in the figures,  $\langle x \rangle x$  and  $\langle x \rangle x$  values will be set to half of x, whereas  $\langle x \rangle x$  and  $\langle x \rangle x$  values will be set to x.

No inferential statistical analyses are planned.

## 8.7. Safety and Tolerability Assessments

#### 8.7.1. Adverse Events

All AEs will be coded using the Medical Dictionary for Regulatory Activities (MedDRA) Version 22.0 (or higher if upversioned during the study).

A treatment-emergent adverse event (TEAE) will be defined as an AE that starts during or after dosing (Part A) or the first dose (Part B), or starts prior to dosing (Part A) or the first dose (Part B) and increases in severity after dosing (Part A) or the first dose (Part B).

A treatment-related TEAE will be defined as a TEAE with a relationship of possibly related or related to the study treatment, as determined by the investigator.

All AEs will be listed. In addition to the data recorded in the database, the listings will include derived onset time and duration. Onset time will be calculated from the time of dosing TEAEs only.

The frequency of subjects with TEAEs and the number of TEAEs will be summarized for the following categories:

- TEAEs (overall, serious, leading to discontinuation, and leading to death) by treatment
- TEAEs by severity and treatment
- Treatment-related TEAEs (overall, serious, leading to discontinuation, and leading to death) by treatment
- Treatment-related TEAEs by severity and treatment

The frequency of subjects will be summarized separately for TEAEs and treatment-related TEAEs by the following:

- System organ class, preferred term, and treatment
- Preferred term and treatment
- System organ class, preferred term, day of onset, and treatment (Part B only)

For the AE data the following rules will apply:

- For the derivation of TEAE status: If the start date/time of an AE is incomplete or missing, an AE will be assumed to be a TEAE, unless the incomplete start date/time or the end date/time indicates an AE started prior to dosing (Part A) or the first dose (Part B).
- For the derivation of treatment-related TEAE status: If the study treatment relationship for a TEAE is missing, a TEAE will be assumed to be a treatment-related TEAE.
- For the derivation of onset time: If the start date/time of an AE is missing, onset time will not be calculated. If the start date/time of an AE is incomplete, where possible, the minimum possible onset time will be calculated and presented in '≥DD:HH:MM' format (eg, if the date/time of dosing is 01MAY2019/08:00 and recorded start date/time of an AE is 03MAY2019, then the minimum possible onset time will be calculated by assuming the an AE started at the first hour and minute of 03MAY2019 [03MAY2019/00:00], thus will be presented as onset time ≥01:16:00 in the listing).

• For the derivation of duration: If the end date/time of an AE is missing, duration will not be calculated. If the start or end date/time of an AE is incomplete, where possible, the maximum possible duration will be calculated and presented in '≤DD:HH:MM' format (eg, if the start of an AE date/time is 01MAY2019/08:00 and its recorded end date/time is 03MAY2019, then the maximum possible duration will be calculated by assuming the AE ended at the last hour and minute of 03MAY2019 [03MAY2019/23:59], thus will be presented as duration ≤02:15:59 in the listing).

- For the calculation of summary statistics: If the severity of a TEAE is missing, a TEAE will be counted under the maximum severity possible.
- For the calculation of summary statistics: If a subject experienced multiple TEAEs with the same preferred term for the same treatment, this will be counted as 1 TEAE for that treatment under the maximum severity recorded.

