#### **4.2. Part B**

Part B will comprise a multiple-dose, sequential-group study. Overall, 32 subjects will be studied in 4 groups (Groups B1 to B4), with each group consisting of 8 subjects. Up to 2 additional groups (16 subjects in total) may be included for further assessment of safety and tolerability.

Potential subjects will be screened to assess their eligibility to enter the study within 28 days prior to the first dose administration. Each subject will participate in 1 treatment period only and reside at the CRU from Day -1 until Day 15.

All subjects will return for non-residential visits on Days 18 ( $\pm 2$  days), 22 ( $\pm 2$  days), 25 ( $\pm 2$  days), and 29 ( $\pm 2$  days), and for a poststudy visit on Day 57 ( $\pm 2$  days).

In each of Groups B1 to B4, 6 subjects will receive OLP-1002 and 2 subjects will receive placebo. For all subjects, a single SC dose will be administered on Days 1, 4, 7, 10, and 13. Prior to each dosing occasion a physician will review the available safety and tolerability data from each subject to confirm it is acceptable to continue dosing. The dosing frequency in Part B may be changed following review of data from groups in Part A.

Sentinel dosing will only occur in Part B at dose levels where exposure to OLP-1002 at steady state is predicted to exceed exposures that have been shown to be safe and well

Covance Study: 8379789

[figure not shown]
tolerated in earlier groups in Parts A or B. In the event of sentinel dosing, 2 subjects (1 active, 1 placebo) will be dosed at least 4 days prior to the remaining 6 subjects (5 active: 1 placebo). Safety data for the sentinel subjects from at least 2 additional doses will be reviewed prior to dosing the remaining subjects (i.e. sentinel subjects' safety data after doses 1 and 2 will be reviewed prior to the remaining subjects receiving dose 1). In addition, safety data from each subject will be reviewed by a physician prior to each dose to approve continued dosing.

Doses will be administered in an escalating manner following satisfactory review of safety, tolerability, and PK data up to Day 22 (216 hours post-final dose) from the lower dose levels. Part B may start after a review of the safety, tolerability, and available PK for Groups A1 to A6. The total daily dose administered will not exceed the highest single dose given in Part A.

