**Table 2: Presentation of Study Treatments in TFLs (Part B)** 

Group	Study Treatment	Order in TFLs
B1 to B6	Placebo a	1
B1	XX μg OLP-1002	2
B2	XX μg OLP-1002	3
В3	XX μg OLP-1002	4
B4 b	XX μg OLP-1002	5
$\mathrm{B5^{b}}$	XX μg OLP-1002	6
B6 b	XX μg OLP-1002	7

<sup>a Placebo will be pooled across all groups

The TFLs will reflect the actual treatments received, and dose levels will be displayed in increasing order. The following footnote will be applied in all applicable Part B TFLs: "Dosing regimen was a single subcutaneous dose administered on Days 1, 4, 7, 10 and 13."

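### The AE counting rule in SAP Section 8.7.1 turns the promised number of TEAEs into a count of distinct subject-by-preferred-term pairs

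*SAP*

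**What the plan says.** SAP Section 8.7.1 sets out two families of AE tables. The first reports subjects and events side by side: "The frequency of subjects with TEAEs and the number of TEAEs will be summarized for the following categories". Those categories are all TEAEs (with serious, discontinuation and death subsets), TEAEs by severity, and the same two for treatment-related TEAEs.

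The second family reports subjects only: "The frequency of subjects will be summarized separately for TEAEs and treatment-related TEAEs by the following". One of its tables is by "System organ class, preferred term, day of onset, and treatment (Part B only").

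The section closes with data-handling rules. The last one is addressed to summary statistics in general. For a subject who had "multiple TEAEs with the same preferred term for the same treatment, this will be counted as 1 TEAE", and the one event kept takes the worst severity on record. The rule names no table or column to which it does not apply.

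In Part B (Section 4.2), "a single SC dose will be administered on Days 1, 4, 7, 10, and 13". Table 2 in Section 6.2 gives one treatment name per dose level, and the footnote prescribed below it for the Part B outputs describes the whole course: "Dosing regimen was a single subcutaneous dose administered on Days 1, 4, 7, 10 and 13".

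**The concern.** Section 8.7.1 separates subject counts from event counts, so the number of TEAEs is meant to tell the reader something that the subject frequency does not. The usual collapsing convention concerns subjects: a subject with several events of one term is counted once, at worst severity. The rule here is written about events. Its unit is one TEAE rather than one subject, and it covers summary statistics in general. It therefore also reaches the columns that are supposed to count events.

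In those columns two things follow. Recurrences of a term in the same subject are not counted, and the single event that remains carries the highest severity, so milder occurrences drop out of the breakdown by severity. In Part B the same treatment covers all five doses, so an event that returns after each dose is reduced to one.

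Incidence and severity of AEs is the first-listed primary endpoint (Section 3.1), and no inferential safety analysis is planned (Section 8.7.8). The descriptive tables carry the safety result, so a column in them should contain what its label says.

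**Working it through.** The SAP states no event rate or expected count, so there is no figure of its own to reproduce. The check applies the rule literally and compares the result with a full event count.

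**Inputs from the SAP**
- Doses per subject in Part B: 5 (Section 4.2).
- Subjects per Part B group: 6 active and 2 placebo (Section 4.2). Placebo is pooled, so B1 to B4 give 4 × 2 = 8 placebo subjects.
- Unit of collapse: subject × preferred term × treatment (Section 8.7.1, last rule). One treatment label covers all five doses (Section 6.2).

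**Assumed input**
- r, the mean number of occurrences of a preferred term per subject who has it. The SAP does not give it. The range 1 to 5 is used, with 5 meaning one occurrence after every Part B dose.

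**Step 1: event counts.** Let P be the number of distinct subject-by-term pairs. A full count gives P × r events and the rule gives P. The undercount is (P × r - P) / (P × r) = 1 - 1/r.

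| r | Undercount |
|---|---|
| 1 | 0% |
| 1.5 | 33% |
| 2 | 50% |
| 3 | 67% |
| 5 | 80% |

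**Step 2: the upper end in Part B.** Suppose every subject has one event of one term after each dose.
- One active group: 6 × 5 = 30 events, shown as 6. Undercount 1 - 6/30 = 80%.
- Pooled placebo, B1 to B4: 8 × 5 = 40 events, shown as 8. Undercount 1 - 8/40 = 80%.

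At equal r the proportional loss is the same on active and placebo.

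**Step 3: severity.** Take one subject with four mild events and one moderate event of the same term. A full count gives 4 mild and 1 moderate. The rule gives 0 mild and 1 moderate.

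**Step 4: day of onset (Part B).** This table counts subjects. The collapse rule contains no onset day, so two readings are open. In the example of Step 2, counting a subject on each onset day gives 6 × 5 = 30 subject-day entries per active group. Collapsing to one record per subject and term first gives 6 entries, on a day that the SAP does not define. The text does not decide between them.

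**Step 5: what the rule does not touch.** A subject counts once in a subject frequency whether or not repeats are collapsed, so subject incidence is unchanged. Every AE is listed with derived onset time and duration (Section 8.7.1). Injection site findings have their own summary tables by timepoint (Section 8.7.6). In Part A each subject has a single dose, so fewer recurrences are likely, but the rule works in the same way.

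**The case against.** The strongest reply is that the author probably meant the conventional rule for subject-frequency and maximum-severity tables, and that the TFL shells, which Section 1 names as the detailed description of the outputs and which are not at hand, may settle the counting. That may be so, but the SAP text says neither, and a programmer who follows it literally produces the collapsed count.

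It can also be said that the number is defined, since the rule is disclosed, and that incidence normally means subjects affected. Both points are fair. They limit the harm to the event columns, but those columns would still be labelled as something they do not contain.

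Some stronger inferences are tempting, and the document does not support them.
- *Recurring injection reactions would become invisible.* Section 8.7.6 tabulates local pain, redness, swelling, tenderness, bruising and ulceration by timepoint, and requires AE recording only for Grade 3 or above and for ulceration. Recurrent local reactions would still be seen; the exposure lies mainly with other recurring AEs.
- *The bias falls mostly on the active arms.* The rule applies equally to Part B placebo, which has the same five-injection schedule, and the SAP gives no AE rates.
- *80% is the expected undercount.* It is the upper end of an assumed range and needs recurrence after all five doses.
- *The day-of-onset table necessarily loses recurrences.* It counts subjects, and the rule does not expressly confine a subject to one onset day. This is an ambiguity, not a demonstrated loss.

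Nor does any stated decision rest on the event count. Dose escalation uses a review of all available safety data (Section 9).

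**Conclusion.** The point holds for the number-of-TEAEs columns. Section 8.7.1 promises an event count and then prescribes a rule that yields distinct subject-by-preferred-term pairs instead. The size is 1 - 1/r: 0% if no term recurs within a subject, 50% at two occurrences on average, 80% at five. The range for r is an assumption, since the SAP gives no recurrence rate. Event counts by severity also lose milder occurrences whenever a more severe one of the same term exists in that subject. Part B is most exposed because one treatment label spans five doses.

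For the Part B day-of-onset table, the conclusion is only that the SAP leaves open how the rule applies.

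Because no data are lost and subject incidence stands, this is a should-fix wording error rather than a threat to the primary safety conclusions.

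**What to change.** Amend Section 8.7.1 in three places, and align the TFL shells.

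1. Restrict the collapse rule to subject frequencies: a subject with several TEAEs of one preferred term on one treatment is counted once for that term, at the highest severity recorded.
2. State that the number-of-TEAEs columns count every TEAE, each under its own severity, including in the treatment-related and by-severity tables.
3. State that in the Part B day-of-onset table a subject is counted once per preferred term per onset day, so the same subject can appear on more than one day.

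The cost is a few sentences of SAP text and minor programming. No additional data are needed. The change should be made before database lock, the point by which Section 1 requires the SAP to be final.
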